#### 7.1.2 REVISED SAMPLE SIZE (APPLICABLE AFTER JANUARY 2018)

Due to the observed low event rate it was decided to abandon the group sequential design. It was clear from the blinded (aggregate) data that the overall population, subdivided by risk of primary outcome into 4 subpopulations by VTE risk crossed with age. i.e. Subpopulation #1 <65 years,

moderate risk of VTE; subpopulation #2 <65 years, high risk of VTE; subpopulation #3 ≥ 65 years at moderate VTE risk; subpopulation #4 ≥ 65 years at high VTE risk. ( With around 250 randomised overall in subpopulation 1 (<65, moderate VTE risk) with zero expected events (0 events observed in the first 180 randomised to Dec 2017), very few events in subpopulation 2 (<65, high VTE risk; around 750 randomised to Dec 2017, observed event 3/510 or 0.6% in the first 510 randomised); virtually no-one randomised into subpopulation 3 (≥65, moderate VTE risk); only 12 randomised to Dec 2017 (this subpopulation will be reported descriptively with no further consideration of formal sample size or inference), and for subpopulation 4 (≥65, and high VTE risk) 750 in subpopulation 4 (306 randomised to Dec 2017 with 11 events observed), the study will not observe sufficient events in total or specifically in subpopulation 4 (the only subpopulation still open to recruitment) to make a re-application of the sequential design sensible.

We have considered (as at Dec 2017) the implications for the sample sizes for the 4 subpopulations, and the Table below gives the detectable non-inferiority margins for indicative sample sizes (at 90% power and a 1-sided level of significance of 2.5%):

Subpopulation	Subpopulation #	Expected number randomised	Assumed event rate	Detectable non-inferiority margin
<65, Moderate	1	258	0.1%	1.30%
<65, High	2	733	0.6%	1.85%
≥65, Moderate	3	12	N/A	N/A
≥65, High	4	912	3.6%	4.0%

Note that these revised sample size calculations do not adjust for multiple comparisons; nor do they adjust for the original group sequential alpha spending (since no interim analyses took place). See Appendix 3- Rationale for Statistical Changes to the Protocol for further details.

The funder agreed to the revised sample size of 912 in subpopulation 4 in April 2018. The other 3 subpopulations (1-3) were closed to any further recruitment at this time, and we will analyse all available data in these 3 subpopulations.

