### **7.2.2 REVISED DATA ANALYSIS (APPLICABLE AFTER JAN 2018)**

A single final analysis and reporting of the trial will occur in line with V2.0 of the Statistical Analysis Plan which was revised from version 1.0 (March 2016) in December 2018.

Under the revised analysis, subpopulations 1-4 as described in Appendix 3 will be analysed separately. Due to simplification it is no longer necessary to consider a group sequential design.

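### Protocol 7.1.2: the margins of 1.30% and 1.85% for subpopulations 1 and 2 do not carry the stated 90% power, because a large-sample formula was used where 0.26 and 4.4 events are expected

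*Protocol*

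**What the plan says.** Protocol section 7.1.2 replaces the group sequential design with four subpopulations defined by age and VTE risk. It says that "the Table below gives the detectable non-inferiority margins for indicative sample sizes (at 90% power and a 1-sided level of significance of 2.5"%). The relevant rows, in the order group, number, expected number randomised, assumed rate and margin, are "<65, Moderate 1 258 0.1% 1.30"%, "<65, High 2 733 0.6% 1.85"% and "≥65, High 4 912 3.6% 4.0"%.

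The text above the table reports "0 events observed in the first 180 randomised to Dec 2017" for subpopulation 1, and 3/510 for subpopulation 2. It describes subpopulation 1 as "With around 250 randomised overall in subpopulation 1 (<65, moderate VTE risk) with zero expected events". Subpopulation 3, with 12 patients, is set aside for description without inference; subpopulations 1 and 2 are not. The note under the table warns only that multiple comparisons and the abandoned alpha spending were not adjusted for. It names no formula and gives no warning about small counts.

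Section 7.2.2 adds that "subpopulations 1-4 as described in Appendix 3 will be analysed separately".

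**The concern.** A power statement for a risk difference needs enough events for the normal approximation to hold. Here the section expects no events in one group and very few in another, yet gives both a margin of one to two percentage points at 90% power.

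Recruitment to both groups has ended, so the numbers cannot grow to make the statement true. If the figures stay, a report could set a zero-event result in younger moderate-risk patients against a pre-stated 1.30% margin and call it met. That result would in fact be compatible with an absolute excess of almost 3% on LMWH alone.

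**Working it through.** **Inputs.** From the section 7.1.2 table: N = 258 at 0.1%, N = 733 at 0.6%, N = 912 at 3.6%; 90% power, one-sided 2.5%. Allocation is 1:1 (section 3). The table states no allowance for loss; the 10% in section 7.1.1 is used below only as a sensitivity check.

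**Step 1: reproduce the table.** Unpooled normal formula with equal true rates: margin = (1.960 + 1.2816) × √(2p(1−p)/n), with n per arm.

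- Subpopulation 1: 3.2415 × √(2 × 0.001 × 0.999 / 129) = 1.28% (stated 1.30%; exactly 1.30% corresponds to N = 250, in line with the text's round figure).
- Subpopulation 2: 3.2415 × √(2 × 0.006 × 0.994 / 366.5) = 1.85% (stated 1.85%).
- Subpopulation 4: 3.2415 × √(2 × 0.036 × 0.964 / 456) = 4.00% (stated 4.0%).
- Section 7.1.1 fixed design: 3.2415 × √(2 × 0.06 × 0.94 / 968) = 3.50% (stated 3.5% with N = 1936).

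Allowing for 10% loss, 80% power, a one-sided 5% level or a pooled formula does not fit the table better.

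**Step 2: expected events, both arms together.** 258 × 0.001 = 0.26; 733 × 0.006 = 4.4; 912 × 0.036 = 32.8.

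**Step 3: zero events in subpopulation 1.** With 0/129 v 0/129, the score and Newcombe upper 97.5% limits are both z²/(n + z²) = 3.84/(129 + 3.84) = 2.89%. An exact one-arm limit is 1 − 0.025^(1/129) = 2.82%, and Agresti-Caffo gives 2.11%. All exceed 1.30%.

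A direct check agrees: if the true rates were 1.3% v 0%, no events in either arm would still occur with probability 0.987^129 = 18%, far above 2.5%. To exclude 1.30% with zero events would take about 282 (exact) to 292 (score) patients per arm.

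**Step 4: power by enumerating all two-arm binomial outcomes.** Non-inferiority is declared when the upper 97.5% limit is below the margin.

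- Subpopulation 1 at 1.30%: 0.03% (score or Newcombe). The outcomes that pass need an excess of at least three events in the stockings arm, for example 0 v 3.
- Subpopulation 2 at 1.85%: 69% (score or Newcombe), 82% (Agresti-Caffo). Here 0/366 v 0/366 gives a limit of 3.84/(366 + 3.84) = 1.04%, which does exclude 1.85%.
- Subpopulation 4 at 4.0%: 87% (score), 88% (Newcombe).

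With 10% loss, power falls to 0.02% in subpopulation 1 and 63% in subpopulation 2 (score or Newcombe).

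**Step 5: margins with about 90% power (score or Newcombe limit).**

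- Subpopulation 1: power is 88% at 2.9%, stays at about 89% up to 4.2%, and jumps to 99% at 4.3%. The first step is the 0 v 0 outcome becoming a pass (limit 2.89%); the last is 1 v 0 (limit 4.26%).
- Subpopulation 2: 2.4% at 90% power. With 10% loss it is 2.65%.

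**The case against.** The strongest reply is that nothing turns on these two rows. The table calls its sample sizes indicative, the text is open about the scarcity of events, subpopulations 1 to 3 are closed, and the funder agreed only the 912 in subpopulation 4. All of this is correct and lowers the severity. It does not make a printed 90% power true, and the table's only caveats concern other matters.

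A second reply is that the protocol names no formula. That is so; the normal approximation is an inference. It rests on one formula giving rows 2 and 4 and the fixed design of section 7.1.1 to rounding, and row 1 closely. The power results in step 4 do not depend on how the margins were obtained.

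Three stronger readings are tempting, and the document does not support them.

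- A reader might infer that neither group can succeed. That applies to subpopulation 1 only; subpopulation 2 would succeed about 69% of the time.
- A reader might infer that false non-inferiority verdicts will follow. A Wald interval has zero width at 0 v 0 and would declare success in subpopulation 1, with a type I error of about 16% at the margin (4% to 5% in subpopulation 2, depending on whether 366 or 367 per arm is used). But the protocol commits neither to a Wald interval nor to a formal non-inferiority verdict in these groups; it says they will be analysed and refers to SAP V2.0. This is a risk only if such an interval were chosen.
- A reader might take 4.3% as the true margin for subpopulation 1. It is a step caused by discrete outcomes: 88% power is already reached at 2.9%, and with 10% loss the 90% point falls to 3.95%, so fewer patients appear to do better.

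**Conclusion.** The statement "at 90% power and a 1-sided level of significance of 2.5"% is wrong for two rows. For subpopulation 1 the power at 1.30% is about 0%, and no interval considered here other than Wald can exclude that margin even with no events at all. For subpopulation 2 the power at 1.85% is about 69%, so the margin is optimistic rather than unattainable. For subpopulation 4 the approximation is nearly adequate (87% to 88% at 4.0%), and the sample size of 912 is not called into question on this ground.

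These results take the protocol's assumed rates as equal in both arms, 1:1 allocation and no loss to follow-up. The 0.1% in subpopulation 1 is itself weakly supported: 0/180 has a one-sided 97.5% upper limit of 1 − 0.025^(1/180) = 2.0%.

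Severity is moderate. It is a correction to a stated property in two closed groups, not a defect in the continuing recruitment.

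**What to change.** In the section 7.1.2 table, do one of the following.

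- Remove the 90% power label from the rows for subpopulations 1 and 2.
- Restate the two rows from exact enumeration with a score-type limit, noting that they are before loss to follow-up: subpopulation 1 about 2.9% at 88% power, passing 90% only at about 4.3% because outcomes are discrete; subpopulation 2 about 2.4% at 90% power.

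In either case, add a sentence that subpopulations 1 and 2 are reported as estimation only, with event counts by arm and a Miettinen-Nurminen or Newcombe 95% interval for the risk difference, and with no non-inferiority conclusion against 1.30% or 1.85%.

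The cost is two table rows and a sentence. No data collection, recruitment or analysis of subpopulation 4 changes; what is given up is two claims that the numbers cannot support.

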## 1.2 EVIDENCE EXPLAINING WHY THIS RESEARCH IS NEEDED NOW

Recent meta-analysis considering VTE rates in surgical patients receiving pharmaco-prophylaxis and GCS compared with pharmaco-prophylaxis alone (8), while containing a number of methodological shortcomings, concluded that evidence concerning "adding compression to anticoagulation reduces VTE risk is of low quality." To address some of the shortcomings, a systematic review has been undertaken aiming to summarise and assess the quality of existing evidence concerning the benefits of GCS in addition to prophylactic dose pharmaco-prophylaxis in inpatients across all surgical specialties, including orthopaedics (9). Inclusion criteria were: RCTs published within the last 10 years, surgical inpatients, a study arm examining prophylactic dose pharmacological thromboprophylaxis alone (including low molecular weight heparin, fondaparinux, or unfractionated heparin), a study arm examining prophylactic dose pharmacological thromboprophylaxis in conjunction with GCS, and outcome of VTE. A heterogeneity analysis was conducted concerning rates of VTE in the included study arms. 1025 articles were screened of which 27 RCTs were included (7,11-33). Six RCT study arms included patients with GCS in conjunction with prophylactic dose pharmacological thromboprophylaxis, whilst 22 RCT study arms included patients treated with prophylactic dose pharmacological thromboprophylaxis alone. Only one RCT had both its' study arms included in the systematic review. Total number of patients that received prophylactic pharmacological thromboprophylaxis alone was 12,481. Of these patients, 1,292 (10.4%) suffered VTE. The total number of patients that received GCS in

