## 7. STATISTICS AND DATA ANALYSIS

### 7.1 SAMPLE SIZE

#### 7.1.1 ORIGINAL SAMPLE SIZE- APPLICABLE UP TO JANUARY 2018

With a one-sided test at 2.5% level of significance (equivalent to a 2-sided test at 5%) the trial has 90% power to conclude that the single pharmacological intervention is non-inferior to the combined intervention (pharmacology and stockings) assuming an event rate of 6% of VTE at 90 days in the combined group and a non-inferiority margin of 3.5%, and a conservative loss to follow up (i.e. non-evaluable for the primary outcome) rate of 10%. The maximum sample size required under this group sequential design, including allowance for loss to follow up, is a total of 2236.

We assume that the standard of care gives a VTE at 90 days proportion of 6%. Historically, we believe the systematic review supports an untreated rate of at least 15%. We have set the non-inferiority margin at 3.5% (i.e. a pharmacological alone rate under the null hypothesis of not more than 9.5%). We think this is justifiable on the grounds that clinicians would not tolerate more than a 3.5% absolute deterioration in VTE event rate over combination therapy, and that it preserves  $(9-3.5)/(15-6)$  or  $5.5/9$  i.e. 61% of the established treatment effect over no intervention (greater than the 50% minimum usually required by regulatory authorities for non-inferiority studies). At 90% power and using a one-sided 2.5% level of significance (equivalent to a two-sided 5%) level we would need to randomise 1936 participants in a fixed sample approach. We prefer to adopt a group sequential approach, giving 4 equally spaced formal interim analyses for efficacy (at 25%, 50%, 75% and a final analysis at 100% of the information) and one formal interim analysis for futility at 50% information. This flexibility to stop early on either efficacy or futility only marginally increases the maximum sample size to 2012 (4% increase, using East 6.3, Cytel Corporation 2014), a flexibility which is useful given the quality, relevance and uncertainty of the evidence base informing the sample size assumptions. If we conservatively allow for 10% loss to follow up, we would need to randomise no more than 2236 in total.

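### Section 7.1.2 powers subpopulation 4 on an unjustified 4.0-point margin, wider than the 3.5 points that section 7.1.1 says clinicians would accept

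*Protocol*

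**What the plan says.** Protocol section 7.1.1, headed as applying up to January 2018, assumes 6% VTE on combined prophylaxis and sets a margin of 3.5 percentage points, so the null rate on LMWH alone is 9.5%. It gives two reasons. The first is clinical: "clinicians would not tolerate more than a 3.5% absolute deterioration in VTE event rate over combination therapy". The second is effect retention: with an untreated rate of at least 15%, 3.5 points keeps 5.5/9 = 61% of the effect, described as "greater than the 50% minimum usually required by regulatory authorities for non-inferiority studies".

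Section 7.1.2, which applies after January 2018, abandons the group sequential design and splits the population into four. It states that "the Table below gives the detectable non-inferiority margins for indicative sample sizes (at 90% power and a 1-sided level of significance of 2.5"%). The row for subpopulation 4 reads "≥65, High 4 912 3.6% 4.0"%. The 3.6% matches the blinded count in that group, "306 randomised to Dec 2017 with 11 events observed". Section 7.1.2 adds: "The funder agreed to the revised sample size of 912 in subpopulation 4 in April 2018".

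Neither section 7.1.2 nor Appendix 3, which is there to explain the statistical changes, gives a clinical or retention argument for 4.0 points. Neither withdraws the 3.5-point tolerance. Section 7.2.2 refers the final analysis to SAP V2.0.

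**The concern.** The margin decides what a non-inferiority trial may conclude. Here the protocol states an absolute limit of tolerance and then plans its 90% power for the main remaining comparison on a wider figure, although the assumed event rate is lower (3.6% against 6%). A margin larger than the assumed event rate means that the true rate to be ruled out is more than double the rate under standard care.

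The supporting argument was not carried over either. The 61% was worked out for a 6% treated rate and was not redone for 3.6%. A reader of the final report could not tell from the protocol whether the subpopulation 4 result should be judged against 3.5 or 4.0 points, and some plausible results fall between the two.

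**Working it through.** **Inputs.** One-sided 2.5%, 90% power, 912 in total, 3.6% and 4.0 points (section 7.1.2); 1:1 allocation (section 6.1), so 456 per arm; 6%, 3.5 points, 15% untreated and 10% loss (section 7.1.1). Section 7.1.2 states no loss allowance.

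**1. Reproduce the plan's figures.** With unpooled variance and a true difference of zero:

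- Standard error = sqrt(2 × 0.036 × 0.964 / 456) = 0.01234.
- Detectable margin = (1.960 + 1.282) × 0.01234 = 0.0400, or 4.0 points. This agrees with the table.
- In the other direction, a 4.0-point margin needs 455.8, so 456 per arm, or 912.
- The same formula gives 1936 for the original fixed design (6%, 3.5 points), as stated.
- It gives 1.28 points for 258 patients at 0.1% (table 1.30) and 1.85 points for 733 at 0.6% (table 1.85).
- For subpopulation 4, adding 10% loss to this formula would need 1013, and a Farrington-Manning score calculation 1029. Of the methods tried, only the unpooled formula with no loss allowance gives 912.

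**2. Power at 3.5 points.**

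| Evaluable | Margin | Margin/SE − 1.96 | Power |
|---|---|---|---|
| 912 | 4.0 | 1.282 | 90.0% |
| 912 | 3.5 | 0.877 | 81.0% |
| 821 (10% loss) | 4.0 | 1.116 | 86.8% |
| 821 (10% loss) | 3.5 | 0.732 | 76.8% |

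Ninety per cent power at 3.5 points would need 1192 evaluable, or 1192/0.9 = 1325 randomised.

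**3. What each margin allows as a true rate.**

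- Original design: 9.5/6 = 1.58.
- 4.0 points at 3.6%: 7.6/3.6 = 2.11.
- 3.5 points at 3.6%: 7.1/3.6 = 1.97.

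**4. Retention at 3.6%.** This depends on the untreated rate, which section 7.1.2 does not give, so two assumptions are shown:

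- If the 15:6 ratio holds, the untreated rate is 3.6 × 15/6 = 9.0% and the effect is 5.4 points. Then 4.0 keeps 1 − 4.0/5.4 = 26%, and 3.5 keeps 1 − 3.5/5.4 = 35%.
- If the untreated rate stays at 15%, the effect is 11.4 points and 4.0 keeps 1 − 4.0/11.4 = 65%.

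**5. Whether the choice can change the verdict.** Take 16/456 events on combined treatment (3.5%) and a simple Wald 95% interval for the difference:

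| Events on LMWH alone | Upper limit (points) | Below 3.5 | Below 4.0 |
|---|---|---|---|
| 20 | 3.40 | yes | yes |
| 21 | 3.66 | no | yes |
| 22 | 3.91 | no | yes |
| 23 | 4.16 | no | no |

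With 21 or 22 events the two margins give opposite conclusions.

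**The case against.** The strongest reply is that 4.0 is not stated to be the decision margin. Section 7.1.2 calls it *detectable* for an indicative sample size, and SAP V2.0 may name the threshold. The 3.5-point tolerance also sits under a heading that ends in January 2018 and was argued at a 6% rate. This stands as a limit on the claim: the protocol cannot be said to have adopted 4.0 as its threshold. It does not remove the inconsistency. No other margin is given for the revised design, the 90% power rests on this one, and the dated heading does not explain why a wider absolute loss would become acceptable at a lower event rate.

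A reader might draw four stronger conclusions that the documents do not support:

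- *That 4.0 was chosen to fit 912 patients.* The wording of section 7.1.2 suggests it, but a round 4.0-point margin also gives exactly 2 × 456, so the arithmetic does not settle the direction.
- *That the trial could call an observed 7.6% against 3.6% non-inferior.* It could not. With 16/456 on combined treatment, the most that passes 4.0 is 22/456 (4.8%, a ratio of about 1.4). If 7.6% and 3.6% are the true rates, the chance of a false claim is the nominal 2.5%.
- *That retention falls below 50%.* This depends on the untreated rate; the range is 26% to 65%. Section 7.1.1 attributes its 15% to a systematic review without a reference number. The review described in section 1.2 covers arms on pharmacological prophylaxis ("22 RCT study arms included patients treated with prophylactic dose pharmacological thromboprophylaxis alone", the others adding stockings), but the documents do not establish that this is the review meant.
- *That the crude rates in section 1.2 measure a stocking effect.* They pool arms from different trials. Only one trial contributed both arms, and the protocol says heterogeneity ruled out summary estimates.

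It is also fair to say that returning to 3.5 points does not cure the relative-scale problem, since the allowed ratio falls only from 2.11 to 1.97.

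**Conclusion.** The point holds as an inconsistency in a figure on which the conclusion depends. Section 7.1.2 plans subpopulation 4 on 4.0 points without justification, 0.5 points above the unretracted tolerance in section 7.1.1 and above the assumed 3.6% rate itself. Judged at 3.5 points, the stated 90% power becomes 81%, or 77% with 10% loss. Even at 4.0 points it is 87% once 10% loss is allowed for. The true ratio to be excluded rises from 1.58 to 2.11.

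These figures assume the unpooled formula that reproduces the protocol's own numbers, 3.6% in both arms, and the 10% loss rate of the original design, since none is stated for the revised one. The retention figures rest further on an assumed untreated rate. Whether SAP V2.0 names a different decision margin cannot be judged from the protocol.

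**What to change.** 1. Reconcile sections 7.1.1 and 7.1.2. State that the subpopulation 4 verdict is judged against a margin no wider than 3.5 points, unless a wider one is justified on both absolute and relative scales. In either case, report the ratio that the margin allows.
2. Restate power at 3.5 points as 81% with 912 evaluable and 77% with 10% loss. If 4.0 is kept for any purpose, give its power with 10% loss as 87%.
3. Label the table's margins, including 1.30% and 1.85% for subpopulations 1 and 2, as the precision available and not as thresholds for a non-inferiority claim.
4. Redo the retention statement for the 3.6% rate with the untreated-rate assumption stated, or limit the 61% to the original design.
5. Make SAP V2.0 agree.

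The cost is wording in the protocol and SAP, with no additional patients. The drawback is that the stated power is less favourable. Restoring 90% at 3.5 points would need about 1325 randomised, which this fix does not require.

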## **7.2 DATA ANALYSIS**

### **7.2.1 ORIGINAL PLANNED DATA ANALYSIS**

All statistical aspects of the trial will be governed by a comprehensive Statistical Analysis Plan (SAP), which will be authored by the trial statistician and approved by both the Trial Steering Committee (TSC) and Independent Data Monitoring Committee (iDMC). The final sample size will be determined by the pre-specified group sequential design, and there will be a single final analysis and reporting of the trial at that point. As a non-inferiority design, both an Intention to Treat (ITT) and a suitably specified Per Protocol analysis will be presented, with primacy given to the ITT approach (albeit it can be that for a non-inferiority design the Per Protocol approach is the more conservative under the null hypothesis). Missing data will be kept to a minimum by good design and conduct, including evidence based processes to maximise retention. It is expected that those missing primary outcomes will be <10% but nonetheless the robustness of the findings under the ITT approach will be assessed by adjusting for these missing data using Rubin's multiple imputation approach under an assumption of missing at random. The primary outcome (VTE at 90 days, Yes/No) will be analysed using a mixed effects logistic regression, with centre as a random effect, VTE risk (moderate vs high) and other to be pre-specified baseline factors as covariates. Secondary outcomes will be assessed in a similar fashion with generalised linear models appropriate to the distribution of the outcome. The level of statistical significance will be taken to be a nominal 0.05. We will undertake for the record the analysis of cohorts 1, 2 and 3 on those recruited prior to 20th December 2017 in line with the original data analysis plan v1.0. Under the new analysis, cohorts 1-4 will be analysed separately. The group sequential analysis is abandoned.

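### Protocol 7.1.2 labels 912 as the number randomised to subpopulation 4, but 912 is the evaluable number for 90% power at 4.0 points, so no allowance for loss remains

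*Protocol*

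**What the plan says.** The table in protocol section 7.1.2 gives detectable margins for indicative sample sizes "at 90% power and a 1-sided level of significance of 2.5" per cent. For subpopulation 4 (aged 65 or over, high VTE risk) it shows 912, an assumed event rate of 3.6% and a margin of 4.0%. The column holding 912 is headed "Expected number randomised". Below the table the figure becomes the target: "The funder agreed to the revised sample size of 912 in subpopulation 4 in April 2018".

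The note under the table names two adjustments that were not made, for multiple comparisons and for the abandoned sequential alpha spending. It says nothing about loss to follow-up.

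Section 7.1.1 did allow for loss: "If we conservatively allow for 10% loss to follow up, we would need to randomise no more than 2236 in total". It defines that loss as being non-evaluable for the primary outcome. Section 7.2.1 adds: "It is expected that those missing primary outcomes will be <10" per cent.

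The narrative above the table in 7.1.2 also contains "750 in subpopulation 4 (306 randomised to Dec 2017 with 11 events observed", without relating the 750 to the 912.

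**The concern.** A number of participants randomised and a number of participants analysed are different quantities, and power depends on the second. If 912 already equals the analysed number required, any missing primary outcome takes power below the stated 90%.

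This concerns the only subpopulation still open to recruitment, and the figures taken to the funder. A reader who has seen the 10% allowance in 7.1.1, and then a note in 7.1.2 listing what was left out, would reasonably assume that the allowance was still in the number.

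**Working it through.** **Inputs.** One-sided 2.5%, 90% power, and for subpopulation 4 N = 912, event rate 3.6% and margin 4.0% (all 7.1.2). 1:1 allocation (6.1). 10% non-evaluable, 6% event rate, 3.5% margin, and totals of 1936, 2012 and 2236 (7.1.1). The 3.6% is consistent with the "306 randomised to Dec 2017 with 11 events observed" in 7.1.2: 11/306 = 3.6%.

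**Formula.** With equal true rates p in both arms, unpooled variance and margin m, the total evaluable number is

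N = 4 × (1.960 + 1.282)² × p(1 − p) / m², with (1.960 + 1.282)² = 10.507.

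**Step 1: confirm the method on 7.1.1.** N = 4 × 10.507 × 0.06 × 0.94 / 0.035² = 1935.1. Rounded up to equal arms of 968 this is 1936, the protocol's fixed-sample figure. The allowance for loss then comes last, on the group sequential maximum: 2012 / 0.9 = 2235.6, stated as 2236.

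**Step 2: reproduce the subpopulation 4 row.** N = 4 × 10.507 × 0.036 × 0.964 / 0.04² = 911.6, or 456 per arm and 912 in total. The row is reproduced with no inflation.

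**Step 3: check the other rows.** The detectable margin is 3.2415 × √(4p(1 − p)/N).
- Subpopulation 2: N = 733, p = 0.006 gives 1.85% (stated 1.85%).
- Subpopulation 1: N = 258, p = 0.001 gives 1.28% (stated 1.30%).

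Both fit with zero loss, so the omission runs through the whole table.

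**Step 4: apply loss to 912 randomised.** SE = √(4 × 0.036 × 0.964 / N). Power = Φ(0.04/SE − 1.960). Margin at 90% power = 3.2415 × SE.

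| Loss | Evaluable | SE (points) | Power at 4.0 points | Margin at 90% power |
|---|---|---|---|---|
| 0% | 912 | 1.234 | 90.0% | 4.00 points |
| 5% | 866 | 1.266 | 88.5% | 4.10 points |
| 10% | 821 | 1.300 | 86.8% | 4.22 points |

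For the 10% row: 0.04/0.01300 − 1.960 = 1.116, and Φ(1.116) = 0.868.

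**Step 5: the other rows at 10% loss.** Subpopulation 2 (660 evaluable) moves from 1.85% to 1.95%. Subpopulation 1 (232 evaluable) moves from 1.28% to 1.34%.

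**Step 6: the size that would keep 90%.** 912 / 0.9 = 1013.3, or 1014 in equal arms. This shows the scale of the omission and is not a proposal to recruit more.

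**Step 7: the 750.** It is not the number randomised to December 2017, which is 306. Nor is it 912 after 10% loss, which is 821; it would take 1 − 750/912 = 17.8% loss to reach it. The text offers no other derivation.

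**The case against.** The strongest reply is that the 10% is not a forecast. Section 7.1.1 calls it conservative and 7.2.1 expects missing outcomes to stay below it. Both sections are marked as original, and 7.1.2 restates no rate. The revised table is also offered as indicative. On this view 86.8% is near the bottom of the protocol's own range, and a margin moving from 4.0 to at most 4.2 points would change no decision.

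Much of this stands. The shortfall is conditional and modest: about 1.5 points of power at 5% loss and about 3 at 10%. The arithmetic gap does not depend on the 10%, however. With 911.6 needed and 912 randomised there is no slack, so any loss at all takes power below 90%. The 10% is also the only loss allowance in the document, and nothing withdraws or replaces it. Calling the table indicative does not alter a column that says randomised, or the adoption of 912 as the agreed target.

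A reader might go further in two ways that the protocol does not support. One is to conclude that the trial is seriously underpowered or must recruit more; the sizes above do not show that. The other is to treat 750 as a rival sample size that leaves the power claim without a clear N. The 90% and the 4.0% sit in one table row with 912, and the funder sentence repeats 912. No power, margin or target is attached to the 750. It stands in a broken sentence explaining why too few events would accrue to resume the sequential design. It may be an earlier projection, or a repeat of the similar figure given there for subpopulation 2; the text does not say.

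**Conclusion.** The point holds. The 912 in section 7.1.2 is an evaluable requirement labelled as a number randomised, and the allowance for loss used in 7.1.1 was dropped without comment. The stated 90% power at 4.0 points is correct only with complete primary outcome data. It is about 88.5% at 5% loss and about 87% at 10%; equivalently, at 10% loss the margin detectable with 90% power is 4.2 points.

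These figures assume the unpooled normal formula that reproduces the protocol's own numbers, a true event rate of 3.6% in both arms, and loss spread equally between arms. The rate of loss in subpopulation 4 is not given, so 5% to 10% is an illustrative range whose upper end is the protocol's own allowance. The matter is not left to the analysis plan, because the protocol itself states the number, power and margin. The 750 is a separate, unexplained inconsistency of an editorial kind.

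**What to change.** Keep 912 randomised. In the subpopulation 4 row, add the evaluable number and state what it delivers: at 10% loss, about 821 evaluable, with about 87% power at 4.0 points or a 4.2-point margin at 90% power. If the non-evaluable rate observed to date is available, use it in place of 10% and say so.

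Treat subpopulations 1 and 2 the same way; at 10% loss their margins become about 1.34% and 1.95%. Add loss to follow-up to the note under the table, so that the note says what was and was not allowed for.

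Separately, correct the 750 or explain how it relates to 912.

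The cost is an edit to one table and its surrounding text. No further recruitment and no change to the analysis is needed; the stated power or margin becomes slightly less favourable.
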